RESEARCH PROTOCOL TEMPLATE INVESTIGATOR INITIATED TREATMENT TRIALS

Title of Project: Utility of three-dimensional transesophageal echocardiography in right ventricular function assessment in surgical aortic valve replacement, mini-sternotomy aortic valve replacement, and transcatheter aortic valve replacement

Principal Investigator: [name]; Department of Anesthesia

Co-Investigators: [name]; Department of Anesthesia
[name]; Department of Anesthesia
[name]; Department of Anesthesia
[name], DO; Department of Anesthesia
[name], DO; Department of Anesthesia
[name]; Department of Medicine
[name]; Medical Student

Abstract

Objective: Right ventricular (RV) function is known to be a critical factor to determine postoperative outcome in cardiac surgery, and echocardiography plays an important role in RV function assessment.¹⁻² In the previous studies, RV function was reported to be more reduced in surgical aortic valve replacement (SAVR) than transcatheter aortic valve replacement (TAVR), but its assessment was performed by 2-dimensional echocardiography.^{3,4} On the other hand, three-dimensional (3D) echocardiography has been the gold standard to assess RV systolic function (EF: ejection fraction), and its intraoperative use is getting more useful in cardiac surgery given recent technological advance in echocardiography machines.¹ However, reality is that we tend to determine RV function based on subjective information or traditional RV function indices, mostly due to unfamiliarity of 3D technique.

In this study, we plan to evaluate intraoperative RV function assessment by 3D transesophageal echocardiography (TEE). We will compare 3D RV EF with other traditional RV function indices ((RV fractional area change (FAC) and tricuspid annular plane systolic excursion (TAPSE)) in SAVR, mini-sternotomy AVR (mini AVR), and TAVR.

A. Specific Aims

1. RV function assessment pre, post cardiopulmonary bypass (CPB), and post chest closure

In 3 arms (arm 1: surgical AVR, arm 2: mini AVR, arm 3: TAVR), baseline pre CPB RV function assessments done after induction of general anesthesia. Post CPB RV function assessment after weaning off CPB and after chest closure is done in the same way as baseline pre CPB RV function assessment. RV function assessment to include 3D RV EF, RV FAC, and TAPSE). In arm 3: TAVR, baseline RV function assessments done

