after induction of general anesthesia. Post TAVR RV assessment is done in the same way as baseline RV function assessment.

2. **Compare 3D RV EF between SAVR, mini AVR, TAVR.**

See Table below for the timing of assessment

	SAVR	Mini AVR	TAVR
Baseline RV (T#1)	Post induction		
Post valve deployment RV (T#2)	Post CPB		Post valve deployment
Post chest closure RV (T#3)	Post chest closure or before extubation		

B. Background and Significance

The importance of postoperative RV function after cardiac surgery has been recognized for more than 30 years, but its assessment has been challenging due to the unique anatomy, physiology, and its position. The RV is pyramid shape, its contraction consists mostly of longitudinal movement, and is less accessible due to its retrosternal position. Thus, RV function assessment has been comprehensive utilizing RV size, RIMP, RV FAC, S', TAPSE, surgeons' "eyeball" impression. With emergence of 3D echocardiography technology, 3D-derived RV EF is the most accurate echocardiographic measure of global RV function¹ Previous study^{3,4} has shown that RV function is more reduced in SAVR than TAVR however their RV assessment was mostly with 2-dimensional echocardiography. This study will be the first study to utilize 3D echocardiography for RV function assessment for SAVR, mini AVR, and TAVR.

C. Preliminary Studies/Progress Report

N/A

D. Research Design and Methods

Design: Prospective clinical trial at single-center tertiary academic hospital.

Participants: Aortic valve surgery patients

Arm 1 (SAVR)

Arm 2 (mini AVR)

Arm 3: (TAVR)

Primary outcome: 3D RV EF

Secondary outcome: Traditional RV function indices (RVFAC and TAPSE)

[figure not shown]
Anesthesia methods: general anesthesia with endotracheal intubation, arterial line, central venous line, pulmonary artery catheter (not for TAVR), TEE.

Anesthesia will be general anesthesia with endotracheal tube, pre-induction arterial line, central venous line, pulmonary arterial catheter (not for TAVR), and TEE; all of which are within standard care, and nothing specific to this study. Choice of the medication including inotropes and vasopressors, and intervention such as transfusion and fluid management will be at each anesthesiologist's discretion.

Measurements:

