Summary statistics will be reported for demographic and clinical data for each group. Similarly, variables are presented as mean \pm SD and median (IQR), when indicated. Categorical data are presented as frequencies and percentages according to the group. Demographic data will be analyzed using the independent t-test, and the Mann–Whitney U test will be used for nominal variables. RV echocardiographic indices will be analyzed using the Mann–Whitney U test (2 groups) or the analysis of covariance (ANCOVA) and pos-hoc pairwise comparisons with Bonferroni correction. For ANCOVA of % change (Timing #3 from #1) in RV indices, covariates included age, gender, norepinephrine equivalent (NE equiv) at Timing #3, CVP at Timing #1, and each RV index at the baseline (Timing #1). Univariate or multivariable logistic regression models were used to assess the association between each echocardiographic index and in-hospital MACCEs. Correlations between continuous variables will be assessed using Pearson's or Spearman's rank correlation tests. Statistical significance is set at $p < 0.05$. All statistical analyses are performed using R version 4.5.1 (The R Foundation for Statistical Computing).

Power analysis

Changes in RV echocardiographic measurements were used to calculate the required sample size, based on a study by Kempny et al.[4] Kempny et al. reported %change of right ventricular strain of - 25.2 (SAVR) and - 20.0 (TAVR) before and after the

procedure, respectively. With the criterion for significance (alpha) set at 0.05 and 80% power for a Mann–Whitney U test, we obtained a sample size of 22 patients per group. The rationale for using RV strain for power analysis is as follows; Sample size calculations for RV strain, RVFAC, and TAPSE provided 22, 7, and 15, respectively. Thus, we decided to use the strictest sample size calculation.

F. Gender/Minority/Pediatric Inclusion for Research

Adult patients over 18 years old are included. Any gender and race patients are included.

G. Human Subjects

1. Inclusion criteria: Adult patients over 18 years old who have mitral valve procedures
Exclusion criteria: patients' refusal, suboptimal echocardiography data
2. Sources of research material in the form of specimens, records or data.
Echocardiography data, medical information in EPIC
3. Plans for recruitment and consent procedures to be followed.
Phone consent will be done in preoperative or actual consent will be obtained in preoperative holding area.

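### The logistic models for in-hospital MACCE have no stated event count or sparse-event method; if events are few, ordinary fits will often fail or overstate odds ratios, and a penalised model costs only wording

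*Combined protocol and SAP*

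**What the plan says.** The MACCE analysis is one sentence in section E, Statistical analysis: "Univariate or multivariable logistic regression models were used to assess the association between each echocardiographic index and in-hospital MACCEs". The same paragraph sets p < 0.05 as the significance level for all analyses. MACCE appears nowhere else. Section D lists "Primary outcome: 3D RV EF" and "Secondary outcome: Traditional RV function indices (RVFAC and TAPSE"), so MACCE is neither a primary nor a secondary outcome, and neither specific aim in section A mentions it.

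For this model the plan does not give:
- a definition of MACCE or an expected rate;
- a covariate list;
- a rule for choosing between the univariate and the multivariable form;
- a method for sparse events.

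The five covariates named in the paragraph belong to the ANCOVA of percentage change, not to the logistic model.

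The sample size comes from section E, Power analysis: "we obtained a sample size of 22 patients per group". It is based on continuous measures only: "Sample size calculations for RV strain, RVFAC, and TAPSE provided 22, 7, and 15, respectively". Section A describes three arms. The total of 66 is 3 × 22 and is not written in the document.

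**The concern.** A logistic model draws its information from the smaller of the event and non-event counts, not from the number of patients. A study sized for a shift in a continuous index may yield only a handful of in-hospital events. With few events and several predictors, maximum likelihood can fail in two ways. Some fits are separated and have no finite odds ratio. Those that converge tend to give odds ratios too far from 1.

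The study sets 3D RV EF beside RVFAC and TAPSE. A result in which one index reaches p < 0.05 for MACCE and another does not would invite the reading that the first is the better prognostic marker. With few events that contrast could be noise or a product of the fitting method. Leaving the choice between univariate and multivariable open also allows the form to be picked after the results are seen.

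**Working it through.** **The plan's own figure.** The inputs in section E are "change of right ventricular strain of - 25.2 (SAVR) and - 20.0 (TAVR"), a difference of 5.2, and "alpha) set at 0.05 and 80% power for a Mann–Whitney U test". No SD is given and sidedness is not stated. Taking a two-sided test:

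n per group = 2(1.96 + 0.84)² SD² / 5.2² ÷ (3/π)

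SD = 6.0 gives 2 × 7.85 × 36 / 27.04 = 20.9, and 20.9 / 0.955 = 21.9, so 22. Any SD from 5.88 to 6.01 returns 22. The figure is attainable but cannot be confirmed, and no event count enters it.

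**Expected events.** N = 3 × 22 = 66, and expected events = 66 × rate. The document gives no rate, so 5 to 30% is an assumed range. The chance that at least one arm has no event is 1 − (1 − (1 − rate)²²)³. At 5%: 0.95²² = 0.324, and 1 − 0.676³ = 0.69. At 10%: 0.9²² = 0.098, and 1 − 0.902³ = 0.27. An arm without events makes its arm term inestimable by maximum likelihood.

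**Simulation.** N = 66, true odds ratio 2.0 per SD of the index, 800 to 2,000 simulated trials per rate. The five-predictor model is index, age, gender and two arm terms. The plan does not specify this set; it is an illustration. Odds ratios are geometric means over estimable fits, and ranges show the spread over repeated runs.

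| Assumed rate | Expected events | Events per predictor (5) | Five-predictor ML: not estimable | Five-predictor ML: OR | One-predictor ML: not estimable | One-predictor ML: OR |
|---|---|---|---|---|---|---|
| 5% | 3.3 | 0.7 | 67–73% | 2.34–2.55 | 5% | 2.26 |
| 10% | 6.6 | 1.3 | 26–31% | 2.40–2.48 | 0.1% | 2.16 |
| 15% | 9.9 | 2.0 | 9–11% | 2.29–2.32 | 0% | 2.16 |
| 20% | 13.2 | 2.6 | about 2% or less | 2.30 | 0% | 2.08 |
| 30% | 19.8 | 4.0 | about 2% or less | 2.27 | 0% | 2.09 |

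**Dependence on the predictor set.** With five predictors but no arm terms, 40%, 10% and 1% of fits fail at 5, 10 and 15%. The arm terms therefore account for much of the failure rate.

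**Precision.** At a 10% rate, over models with one to seven predictors, the upper 95% limit is typically 6.5 to 8 times the lower one. Power to detect an odds ratio of 2 is 24 to 31%.

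**Penalised alternative.** At 5, 10 and 15%, Firth regression with the same five predictors gives 1.93, 2.05 and 2.04, and fails only in trials with no event. One-predictor Firth gives 1.96 to 2.07 over these rates. Penalisation removes the inflation with or without adjustment.

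**What dropping adjustment would cost.** Section B cites earlier work in which right ventricular function fell more after SAVR than after TAVR. Suppose arm also shifts MACCE risk in the same direction (illustrative shifts of ±0.5 SD in the index and ±0.7 in log-odds). At 5, 10 and 15%, unadjusted Firth then gives 2.31, 2.37 and 2.42, and five-predictor Firth gives 1.81, 2.01 and 2.04.

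**The case against.** The strongest reply is that the failing model is not in the plan. Univariate models are expressly allowed, no logistic covariates are listed, and maximum likelihood is only the ordinary reading of the sentence. Because MACCE is undefined, nothing in the document holds the rate to 15% or less. At 20 to 30% the model can almost always be fitted and the inflation is modest. MACCE is also outside the listed outcomes, so no main conclusion depends on it.

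All of that stands, and it limits the point. A reader might infer that 66 patients cannot support any multivariable MACCE model, or that its odds ratios will be unusable at any plausible rate. The document supports neither inference, since both need an event rate and a covariate set that it does not supply. A reader might also infer that all adjustment should be removed. The Firth results contradict that: the five-predictor penalised model is about as unbiased as the one-predictor version, and dropping arm can bring bias back.

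The reply does not answer the omission itself. Nothing in the plan shows that the events will suffice, and nothing says what to do if they do not. Keeping only the univariate form does not fully help either, since one-predictor maximum likelihood still gives 2.16 to 2.26 at rates of 5 to 15%.

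**Conclusion.** The concern holds conditionally. The MACCE models rest on no stated event count. If the in-hospital rate is about 5 to 15%, a multivariable maximum-likelihood model that includes arm has a failure risk running from roughly 70% down to 9%, and it inflates a true odds ratio of 2.0 to about 2.3 to 2.6. With more events or a single predictor, failure is uncommon and the figure is about 2.1 to 2.3.

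These sizes depend on assumptions: the event rates, the true odds ratio of 2.0, the predictor set, and all 66 patients being analysed. Section G excludes suboptimal echocardiography data with no stated allowance, so the analysed number could be lower. The consequence is confined to one unlisted, in effect exploratory, analysis. It is worth correcting because a better method is available for a change of wording.

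**What to change.** Rewrite the MACCE sentence in section E to say the following:

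- State what counts as an in-hospital MACCE and list the events by arm.
- Fit a Firth-penalised logistic model for each index, naming the time point used, and report odds ratios with profile-likelihood 95% intervals.
- Label the analysis exploratory and make no p < 0.05 claim for it.
- Limit the covariates by the number of observed events, under a rule fixed before the data are examined.
- Keep a penalised model adjusted for arm, at least as a sensitivity analysis.
- If events are very few (for example fewer than about 5), report counts only.

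The cost is SAP wording; no extra patients or measurements are needed. The downside is wide intervals and no confirmatory statement about MACCE.

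### The only sample-size justification is for an unadjusted two-group test of RV strain, so 80% power is not established for the three-arm Bonferroni comparison of 3D RV EF

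*Combined protocol and SAP*

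**What the plan says.** All references are to the combined protocol and SAP.

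- **Outcome.** Section D states "Primary outcome: 3D RV EF" and lists RVFAC and TAPSE as secondary. The second aim in section A is to compare 3D RV EF between SAVR, mini AVR and TAVR.
- **Analysis.** Section E (Statistical analysis) gives, for the RV indices, a Mann–Whitney U test for two groups, or ANCOVA with "pos-hoc pairwise comparisons with Bonferroni correction". For % change from T1 to T3, the ANCOVA adjusts for age, gender, norepinephrine equivalent at T3, CVP at T1 and the baseline value of the index.
- **Sizing.** Section E (Power analysis) takes its effect from a published comparison that "reported %change of right ventricular strain of - 25.2 (SAVR) and - 20.0 (TAVR) before and after the" procedure. "With the criterion for significance (alpha) set at 0.05", it reports "80% power for a Mann–Whitney U test, we obtained a sample size of 22 patients per group". It explains the choice of strain thus: "Sample size calculations for RV strain, RVFAC, and TAPSE provided 22, 7, and 15, respectively", followed by "Thus, we decided to use the strictest sample size calculation".

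The plan gives no SD, sidedness or allowance for unusable images. It gives no effect for 3D RV EF and none for mini AVR.

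**The concern.** The sizing and the primary analysis differ in four ways: the index (strain against 3D RV EF), the number of arms (two against three), the significance level per comparison (0.05 against 0.05/3) and the test (Mann–Whitney against ANCOVA). Choosing the largest of three sample sizes is cautious for those three indices. It says nothing about a fourth index that was never sized.

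This is the only justification for the number of patients. A reader who finds no difference in 3D RV EF, particularly in a contrast with mini AVR, may take it as a null result from a trial with 80% power for that question. Nothing in the plan supports that reading.

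**Working it through.** **Inputs from the plan:** n = 22 per group, power 80%, alpha 0.05, difference in % change of strain 25.2 − 20.0 = 5.2 points, three arms and so three pairs, Bonferroni level 0.05/3 = 0.0167. **Assumed:** two-sided testing, because sidedness is not stated.

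**1. The plan's own figure.** The 22 cannot be reproduced independently because no SD is given. It can only be inverted to find the effect it implies.

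- Normal approximation: d = (1.960 + 0.842) × √(2/22) = 0.845, so SD = 5.2/0.845 = 6.16 points.
- Mann–Whitney (effective n = 22 × 3/π = 21.0, noncentral t): d = 0.886, so SD = 5.2/0.886 = 5.87 points.

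Both return 80% at alpha 0.05 by construction. This shows neither that 22 is right nor that it is wrong.

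**2. The same effect at the Bonferroni level, no covariate gain.** Power ≈ Φ(d√(n/2) − z), with z = 2.394 for two-sided 0.0167.

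- Normal: 0.845 × √11 = 2.802; Φ(2.802 − 2.394) = Φ(0.408) = 66%.
- Mann–Whitney with d = 0.886: 64.6% (64.2% by simulation).
- A contrast half as large, for example if mini AVR lies midway: Φ(1.401 − 2.394) = 16%; Mann–Whitney also 16%.
- Size needed for 80% at 0.0167: 2 × (2.394 + 0.842)²/0.845² = 29.3, so 30 per arm. Mann–Whitney also gives 30.

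**3. What 22 per arm detects with 80% power (Mann–Whitney, before covariate adjustment).** 0.89 SD at alpha 0.05; 1.04 SD at 0.0167.

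**4. Covariate gain.** If the covariates explain a share R² of the variance, d becomes d/√(1 − R²). With R² = 0.25: 2.802/√0.75 = 3.235; Φ(3.235 − 2.394) = 80%. The plan states no R².

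**5. The plan's other two sizes, by the same Mann–Whitney method.**

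| Index | Plan's n | Implied d | Power at 22 per arm, 0.0167 |
|---|---|---|---|
| RV strain | 22 | 0.89 | 65% |
| TAPSE | 15 | 1.09 | 84% |
| RVFAC | 7 | 1.68 | over 99% |

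**6. Sensitivity to the missing SD** (assumed values on both sides of the implied 5.9; difference 5.2, 22 per arm, Mann–Whitney).

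| SD | Power at 0.05 | Power at 0.0167 |
|---|---|---|
| 5 | 91% | 80% |
| 8 | 54% | 36% |
| 10 | 38% | 22% |

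None of these figures is a power for 3D RV EF, which would need an effect and an SD that the plan does not give.

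**The case against.** The strongest reply is that the plan claims less than a reader might infer. It states 80% for strain in a two-group test and never attaches that figure to 3D RV EF. This stands: the sentence is not shown to be false, and no arithmetic error has been found.

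Further points on that side:

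- **A reader might infer that the trial is underpowered for its primary outcome.** The documents do not support this. The 65% borrows the strain effect. The two secondary outcomes, which do have sizes, keep more than 80% for SAVR against TAVR after Bonferroni. An SD of 5 would give 80% for the 5.2-point difference as well. The position of 3D RV EF in that range is unknown.
- **The planned ANCOVA may recover the loss.** An R² of about 0.25 would do so for the full effect, and a baseline value is among the covariates. But the power calculation takes no credit for this, and the arms are not described as randomised, so covariate imbalance could reduce the gain.
- **A two-group Mann–Whitney test is also listed.** An unadjusted SAVR–TAVR test is therefore not excluded. The plan does not name it as primary or exempt it from Bonferroni, and the 80% would still refer to strain.
- **A reader might infer that strain is never measured.** The text supports only that it is not a listed outcome or a described measurement. The measurement list is worded as non-exhaustive, and figures are missing from the available text.

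Bonferroni also protects against false positives, so the harm is limited to over-reading a null result.

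**Conclusion.** The concern holds as a mismatch between the sizing and the primary endpoint and analysis. The 80% is not established for 3D RV EF in the three-arm Bonferroni comparison, and no contrast with mini AVR has a planning effect.

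Its size can be given only conditionally. For an effect as large as the one behind the 22, unadjusted power at 0.0167 is about 65% rather than 80%; for half that effect it is about 16%. This rests on two-sided testing, all three pairs being tested, a back-solved SD and no covariate gain. If the 22 came from a one-sided calculation, the implied effect falls to 0.78 SD and the two-sided Bonferroni power to about 52%. The shortfall belongs to the strain-sized effect. It does not show that power for 3D RV EF is low, nor that 22 was miscalculated.

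**What to change.** Rewrite the power paragraph in section E to state that:

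1. the 80% refers to % change in RV strain, SAVR against TAVR, in an unadjusted two-group test at 0.05, and does not carry over to 3D RV EF;
2. 22 per arm detects, with 80% power before covariate adjustment, about 0.89 SD at alpha 0.05 or 1.04 SD at 0.0167;
3. if Bonferroni stays, power for the planning effect is about 65% without covariate gain;
4. the mini AVR contrasts have no planning effect.

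The SD and sidedness behind the 22 should be added so that it can be checked.

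Optionally, name SAVR against TAVR on 3D RV EF as the single primary contrast at two-sided 0.05, with the mini AVR contrasts tested only after it. This is acceptable only if fixed before outcome data are examined. Parts of sections D and E are in the past tense, which leaves open that data already exist; in that case only the rewording should be made.

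Cost: wording only, with no extra patients. The stated power becomes less favourable, and under the optional change the mini AVR contrasts become formally secondary.

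### The written inclusion criterion names mitral valve procedures, although the title, all three arms and the planned comparison concern aortic valve replacement

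*Combined protocol and SAP*

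**What the plan says.** Section G (Human Subjects), item 1, gives the eligibility rule: "Inclusion criteria: Adult patients over 18 years old who have mitral valve procedures". The line that follows is "Exclusion criteria: patients' refusal, suboptimal echocardiography data".

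The rest of the document describes a different population:

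- The title names "surgical aortic valve replacement, mini-sternotomy aortic valve replacement, and transcatheter aortic valve replacement".
- Section A (Specific Aims) defines the groups: "In 3 arms (arm 1: surgical AVR, arm 2: mini AVR, arm 3: TAVR".
- Specific Aim 2 is "Compare 3D RV EF between SAVR, mini AVR, TAVR", and the timing table beneath it has one column for each of those three procedures.
- Section D (Research Design and Methods) states "Participants: Aortic valve surgery patients" and lists the same three arms.
- The power analysis in section E uses inputs for SAVR and TAVR: "change of right ventricular strain of - 25.2 (SAVR) and - 20.0 (TAVR) before and after the" procedure.

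Section F also touches on eligibility, but names no valve: "Adult patients over 18 years old are included. Any gender and race patients are included".

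**The concern.** An inclusion criterion fixes who may be enrolled, and it is the text against which each patient's eligibility would be checked. Here it names a different valve from the one under study. Two things follow if it is applied literally. The patients the trial is about, those having an aortic valve replacement and no mitral procedure, fail it. Patients having a mitral procedure and no aortic one pass it, yet no arm, timing column or planned comparison exists for them.

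If staff instead enrol according to the evident intent, the comparison can go ahead as designed. The record would then show isolated aortic valve patients enrolled against the written criterion, and the trial's formal population would not match the one analysed.

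**Working it through.** This is a question of consistency between passages, so the check was to collect every statement of the population and then test patient types against the rules.

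**Step 1. Which valve does each statement name?**

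| Place in the combined protocol and SAP | Population named |
|---|---|
| Title | Aortic (surgical, mini-sternotomy, transcatheter) |
| Section A, arms | Aortic (all three arms) |
| Section A, Aim 2 and timing table | Aortic (all three procedures) |
| Section D, Participants line and arms | Aortic |
| Section E, power analysis inputs | Aortic (SAVR and TAVR) |
| Section F | No valve named (age, gender, race) |
| Section G.1, exclusion criteria | No valve named |
| Section G.1, inclusion criterion | Mitral |

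G.1 is the only place in the text where the word mitral occurs.

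**Step 2. Does another eligibility statement correct G.1?** No. Section F adds nothing on the procedure. The exclusion criteria remove patients who refuse and those with suboptimal echocardiography data. Neither admits an isolated aortic valve patient or removes a mitral-only one.

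**Step 3. Apply G.1 and the arm definitions to each type of adult patient** (consenting, with adequate images).

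| Procedure | Meets G.1 as written? | Fits an arm? |
|---|---|---|
| SAVR, mini AVR or TAVR, no mitral procedure | No | Yes |
| Mitral procedure only | Yes | No |
| Aortic valve replacement with a mitral procedure | Yes | Yes |
| Neither | No | No |

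Only the third row satisfies both rules. The first row, which the title and aims describe most directly, fails G.1.

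**Step 4. Does any figure in the plan depend on this?** No. The stated 22 patients per group comes from the power analysis, which takes changes in RV strain of −25.2 and −20.0 for SAVR and TAVR (a difference of 25.2 − 20.0 = 5.2 percentage points). Those inputs are already aortic, so correcting G.1 leaves them as they are. The documents give no standard deviation, so the 22 can be neither reproduced nor refuted here, and this point does not rest on it.

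**The case against.** The strongest reply is that this is an obvious slip. The arms are defined by procedure, so a mitral-only patient has no arm, no column in the timing table and no place in Aim 2. The Participants line also restricts the study to aortic valve patients. Read as a whole, the protocol cannot bring such a patient into the comparison. That reply stands as far as it goes: mis-enrolment may be unlikely, and the practical harm is mainly that eligibility on paper would not match enrolment. It does not make the criterion correct, and nothing in sections F or G tells a reader to disregard it.

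Three stronger readings are tempting, and the documents do not support them.

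- *Every planned patient is ineligible, that is 3 × 22 = 66.* The arms are not restricted to isolated aortic valve replacement, so a patient having both procedures would meet G.1 and fit an arm. The documents do not say how many such patients to expect. They also state no total: the 22 per group comes from a calculation based on two groups.
- *The criterion would bias the comparison, because mitral disease affects RV function and would enter the surgical arms only.* The documents neither state such a link nor describe concomitant procedures in any arm.
- *The trial will enrol the wrong population.* The text shows what the rule permits if followed literally. It does not show that staff would follow it against the title, arms and Participants line.

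**Conclusion.** The contradiction is certain from the text, and the formal inclusion criterion is wrong as written. Its reach is this: no isolated SAVR, mini AVR or TAVR patient satisfies G.1, and mitral-only patients satisfy it without belonging to any arm. No count of affected patients and no effect on the results can be derived from the documents.

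The conclusion assumes only that G.1 is read literally. That it is a drafting error is an inference from the consistent aortic wording elsewhere. The correction should be required because a core eligibility rule names the wrong valve, not because mis-enrolment or bias is predicted.

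**What to change.** Reword the inclusion criterion in G.1 so that it matches sections A and D: adults undergoing surgical AVR, mini-sternotomy AVR or TAVR, with the age wording left as it is.

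The cost is a short text amendment and its submission to the IRB. Sample size, outcomes and analyses are untouched. The document does not show whether enrolment has begun. If it has, the sponsor should also record which population was actually screened and enrolled, so that the patients already included can be reconciled with the corrected criterion.

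Separately and optionally, the sponsor could state how aortic valve replacement with a concomitant mitral procedure is handled, since the protocol is silent on it. That is not needed to resolve this contradiction.
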